# Summary project

## 一、 Research Program

Project name	Comparison of clinical efficacy of golden microneedles and 1565nm non-ablative dot matrix laser in the treatment of eyelid pouches
Purpose of the Study	The purpose of this test is to compare the efficacy of golden microneedles and 1565nm non-ablative dot matrix laser in the treatment of eyelid pouches.
Type of study	Randomized, double-blind, self-controlled study
Number of cases	16
Inclusion and Exclusion Criteria	Inclusion Criteria: 

1. Patients with blepharoplasty;

2. Fitzpatrick III-V;

3. Males and females between 18-60 years old.

	Exclusion criteria: 

1. Other diseases that can cause pathological changes in periorbital soft tissue, such as collagen disease, kidney disease, liver cirrhosis, Graves disease, diabetes, scleroderma, hyperlipidemia, myasthenia gravis, Horner syndrome, myosermatitis etc;

2. Other diseases affecting wound healing, such as systemic diseases such as diabetes, heart disease, hypertension, infectious diseases such as tuberculosis, hepatitis, skin diseases, tumors, etc.; such as dry eye syndrome, cataract, glaucoma ophthalmic diseases.

3. Take steroids, vasodilators, anticoagulants (warfarin, non-steroidal anti-inflammatory drugs, aspirin, heparin, etc.) and retinoids 2 weeks before surgery. Local infections on the skin.

	
4. Patients with blepharoplasty, periorbital laser, botulinum toxin type A treatment history, and herpes simplex virus (HSV) infection history 6 months before surgery. History of exposure 2 months before surgery.
 
5. Scar physical, pregnancy, bilateral asymmetrical eye bags. Before entering the group, they were informed of their risks, benefits, and possible complications after the operation, and signed an informed consent.
 
6. Can not guarantee treatment on time, those who fail to cooperate.

Treatment options	
16 patients with blepharoplasty bags, and two bilateral blepharoplasty bags were treated with laser respectively, and subjective adverse reactions (pain, burning, and burnout) were recorded before treatment, 4 weeks after each treatment, and 12 and 24 weeks after the third treatment. Itching, dryness), objective adverse reactions (erythema, pimples, edema, exudation, bleeding, scabbing, infection), patient satisfaction VAS score, visa skin tester, 3D skin test, ultrasound measurement of lower eyelid fat volume every 4 weeks Treat once and treat three times per person.

Efficacy evaluation	
Effectiveness evaluation indicators:
 
 
1. Patient satisfaction
 
2. Wrinkles, texture and pores by VISIA
 
3. 3D data changes
 
4. Ultrasound measurement of BLEs volume.
 
 
Safety evaluation indicators:
 
 
1. Subjective adverse reactions-pain, burning, itching, dryness
 
2. Objective adverse reactions-erythema, pimples, edema, exudation, bleeding, crusting, infection.
 

Statistical	
The pain of the left and right lower eyelids was tested by paired t

methods	test, the changes of various indexes of visia, 3D, and ultrasound were compared with the Wilcoxon symbol rank test of paired samples, and the subjective and objective adverse reactions were tested by $\chi^2$ test.
Study period	2 years

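### The treatment row names only laser although the trial compares two devices, and the pain test compares left with right eyelid, which is not a device contrast under random side allocation

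*Combined protocol and SAP*

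**What the plan says.** All of the relevant text is in the Research Program table.

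- **Project name and purpose.** Both name two devices. The purpose row gives the aim as follows: "compare the efficacy of golden microneedles and 1565nm non-ablative dot matrix laser in the treatment of eyelid pouches". The project name lists the same pair.
- **Type of study.** The design is described in one phrase: "Randomized, double-blind, self-controlled study". The row does not say what is randomised.
- **Treatment options.** After "16 patients with blepharoplasty bags", the row continues: "two bilateral blepharoplasty bags were treated with laser respectively". Laser is the only modality it names. The session rule, "every 4 weeks Treat once and treat three times per person", gives neither a device nor a side.
- **Statistical methods.** "The pain of the left and right lower eyelids was tested by paired t" test. Changes in the VISIA, 3D and ultrasound measures go to a Wilcoxon signed-rank test on paired observations, with no statement of what forms the pair. Adverse reactions go to a χ² test, with no groups named.

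In the text available for review, the section that follows, 二、 Research process, is a heading with nothing under it.

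**The concern.** The Treatment options row is where a reader looks to learn what is done to each eyelid. In the text available, no other row describes treatment. It conflicts with the title and purpose on the basic question of which devices are used. It also leaves the allocation of devices to sides unstated.

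The conflict matters for the statistics because the design is self-controlled. The device effect is estimated within patients, from the difference between the two eyelids, so every paired analysis needs to know which eyelid received which device. The plan gives no such rule, and its one explicit pairing, for pain, is anatomical. Pain could therefore be analysed exactly as written and yield a result that says little or nothing about the devices. The other paired tests could be run on different pairings by different analysts, each consistent with the text.

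**Working it through.** **Step 1: the rows side by side.** The plan gives no figure to reproduce here.

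| Row | Devices named | Link between device and side |
|---|---|---|
| Project name | microneedles, laser | none |
| Purpose | microneedles, laser | none |
| Type of study | none | none (randomised and self-controlled only) |
| Treatment options | laser only | none |
| Statistical methods | none | none (pain by left and right; other pairs undefined) |

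Microneedles appear twice in the text, in the project name and in the purpose. They appear in no row on treatment, efficacy, safety or analysis.

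**Step 2: what a left-against-right pain test estimates.** Assume that one eyelid of each patient gets microneedles and the other gets laser, that the side is chosen at random, and that pain has no inherent left-right difference. Define:

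- d = mean pain on the microneedle side minus mean pain on the laser side;
- p = fraction of patients with microneedles on the left;
- n = 16 patients, from the Number of cases row.

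A patient with microneedles on the left contributes an expected left-minus-right difference of +d. A patient with microneedles on the right contributes −d. The expected mean difference is therefore

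p·d + (1 − p)·(−d) = d(2p − 1).

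For n = 16:

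| Microneedles left / right | p | 2p − 1 | Expected left − right |
|---|---|---|---|
| 8 / 8 | 8/16 = 0.5 | 0 | 0 |
| 10 / 6 | 10/16 = 0.625 | 0.25 | 0.25d |
| 16 / 0 | 1 | 1 | d |

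The left-right difference equals the device effect only if every patient has microneedles on the left, and then the side is not randomised. At an even split it is zero however large d is. The device effect then appears only as extra spread in the differences, because its sign changes from patient to patient. If there were a true left-right difference s, the expectation would be s + d(2p − 1). At 8/8 the test would then estimate s alone.

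**Step 3: the other paired outcomes.** For VISIA, 3D and ultrasound the wording fits at least three pairings: microneedle side with laser side, left with right, and before with after within one eyelid. Only the first is the comparison named in the purpose. Step 2 would apply to these outcomes if left with right were used, but the plan does not say that it is.

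**The case against.** The strongest reply is that this is a drafting or translation slip. The title and purpose both name two devices. The disputed sentence contains the word *respectively*, which makes little sense if both bags receive the same treatment, and laser on both sides would leave nothing to randomise or to self-control. The English is rough throughout, so one phrase should not be read as a precise specification. The Research process section is also empty in the text available, and an allocation scheme may have been lost there.

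Most of this stands. A reader might infer from the treatment row that the plan has no microneedle arm, that 0 of the 32 eyelids would receive microneedles, or that the trial cannot answer its question. The documents do not support those readings. The title, purpose and type of study all point to one device per side, and the count of 0 in 32 only restates the literal sentence as a number. Nor can the treatment row be called the sole description of treatment in the full protocol when a later section may have lost content.

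A reader might also infer that the whole analysis is left against right. That is not supported either. Only pain is labelled by side, and the wording for the Wilcoxon tests is compatible with a device-by-device pairing.

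The objection does not remove the conflict itself. Someone who guesses the intent correctly still cannot recover from these rows which eyelid gets which device. Even if an allocation scheme exists elsewhere, the treatment row would still disagree with the title and purpose, and the pain test would still be specified by side.

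**Conclusion.** Wrong as written, in two linked places. First, the Treatment options row names only laser and so contradicts the project name and purpose. No text available states the device-to-side allocation. One device per side was probably intended, and the point does not depend on any other intent. Second, the pain test compares left with right. Under random side allocation its expected value is d(2p − 1): zero at 8/8 and a quarter of the device effect at 10/6.

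The second result assumes one device per eyelid, random allocation of sides, and no inherent side difference. It needs no alpha, power, effect size or standard deviation, none of which the plan gives. It applies outright to pain only. For VISIA, 3D and ultrasound the fault is narrower: the pair is undefined. The finding concerns the written plan and the text available, not what was done to patients.

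**What to change.** 1. **Treatment options row.** Reconcile it with the project name and purpose. The sponsor should state which study device each eyelid of a patient receives and that the randomisation decides this, if one device per side is what was intended. One sentence.
2. **Record form.** Add a field for the device applied to each eyelid, so that the label is available at analysis. One field.
3. **Statistical methods row.** Define the paired pain test as microneedle side against laser side instead of left against right. Say that the pairs for VISIA, 3D and ultrasound are formed in the same way, each using the change from before treatment. One sentence.

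If the Research process section of the full protocol already holds the allocation scheme, the treatment row can refer to it, but both rows still need correcting. None of this alters the number of patients, the visits or the measurements.

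### Adverse reactions have no stated record until about day 28 after a session and no recall window, so unless the full plan adds an earlier record the between-eyelid tests of short-lived reactions will find almost nothing or rest on memory

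*Combined protocol and SAP*

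**What the plan says.** All the readable text is in the Research Program section of the combined protocol and SAP.

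- **Treatment options row.** Adverse reactions "were recorded before treatment, 4 weeks after each treatment, and 12 and 24 weeks after the third treatment". The sentence is broken: the list of subjective reactions starts before the schedule and resumes after it with "Itching, dryness), objective adverse reactions (erythema, pimples, edema, exudation, bleeding, scabbing, infection), patient satisfaction VAS score". The same row gives the session interval: "every 4 weeks Treat once and treat three times per person".
- **Efficacy evaluation row.** The safety indicators are "Subjective adverse reactions-pain, burning, itching, dryness" and "Objective adverse reactions-erythema, pimples, edema, exudation, bleeding, crusting, infection".
- **Statistical methods row.** "The pain of the left and right lower eyelids was tested by paired t" test, while "the subjective and objective adverse reactions were tested by" chi-squared. Neither test is tied to a time point.
- **Purpose of the Study row.** The aim is to "compare the efficacy of golden microneedles and 1565nm non-ablative dot matrix laser in the treatment of eyelid pouches", so safety is not the stated purpose.

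The readable text mentions no same-day or first-week record, no diary and no recall period. The next section, Research process, shows only a heading.

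**The concern.** Several listed reactions, such as burning, edema, exudation, bleeding and crusting, may well be over within days. The documents give no durations, so this is an assumption. A first record at about day 28 then has two possible meanings, and the text does not choose between them. It may count what is still present at the visit, in which case most short-lived reactions are gone. Or it may ask about the whole interval since the last session, in which case it relies on memory up to 4 weeks old.

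After sessions 1 and 2 the 4-week record also coincides with the next session. The text does not say whether it is taken before or after that day's treatment, so a fresh reaction could be mixed with the residue of the previous one.

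At stake is the between-device comparison of short-lived reactions. A table of near-zero counts could be read as showing that the two devices are equally well tolerated when the data could not have shown otherwise.

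**Working it through.** **Timing.** Sessions fall at about days 0, 28 and 56. The 4-week records fall at about days 28, 56 and 84, each about 28 days after the session it refers to. Reading the pre-treatment record as one taken before every session does not help: before sessions 2 and 3 it is also about 28 days after the previous session.

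**Inputs.** From the documents: 16 patients, hence 16 sides per device, and a chi-squared test for reactions. The documents give no reaction rates, durations, recall or significance level. All of these are assumed below, with a two-sided 5% level. The plan states no power figure to reproduce.

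**Formulas.**
- Fraction captured = persistence + (1 − persistence) × recall.
- With a and b affected sides out of 16 and s = a + b, X² = 32(a − b)² / [s(32 − s)]. Significant if X² > 3.841. With continuity correction, (a − b)² becomes (|a − b| − 1)².
- Chance of a significant result in a given direction = sum of Bin(a; 16, p₁) × Bin(b; 16, p₂) over the qualifying pairs. Sides are treated as independent, as in the planned test.

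Example against zero events: 4 vs 0 gives 32 × 16 / (4 × 28) = 4.57 (p = 0.0325, significant); 3 vs 0 gives 32 × 9 / (3 × 29) = 3.31 (p = 0.069, not significant). At least four affected sides against none are needed.

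**Equal capture, assumed true rates 80% vs 40%, correct direction:**

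| Fraction captured | Expected affected sides | Uncorrected | Continuity-corrected |
|---|---|---|---|
| 100% | 12.8 vs 6.4 | 66.9% | 50.4% |
| 90% | 11.52 vs 5.76 | 55.4% | 39.9% |
| 80% | 10.24 vs 5.12 | 45.6% | 31.0% |
| 55% (10% persist, half the rest recalled) | 7.04 vs 3.52 | 27.7% | 14.3% |
| 20% | 2.56 vs 1.28 | 7.8% | 1.1% |
| 10% | 1.28 vs 0.64 | 1.8% | 0.06% |
| 5% | 0.64 vs 0.32 | 0.2% | <0.01% |

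The last three rows are the present-at-visit reading, with no recall. The 80% and 90% rows represent good, equal recall.

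**Second model for present-at-visit.** Assume exponential durations with mean m days, so persistence at day 28 is exp(−28/m), and true rates of 80% vs 30%. For m = 3, 5 and 7 days, persistence is 0.01%, 0.4% and 1.8%. Chi-squared power is 85% with early capture and at most 0.01% at day 28. For m = 7, the chance of no event on any of the 32 eyelids is (1 − 0.01465)¹⁶ × (1 − 0.00549)¹⁶ = 72%.

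**Unequal recall, assumed equal true rates of 60%.** Persistence is 10% on both sides and recall is 70% vs 30%. Captured fractions are 0.1 + 0.9 × 0.7 = 0.73 and 0.1 + 0.9 × 0.3 = 0.37. Expected affected sides are 16 × 0.6 × 0.73 = 7.01 and 16 × 0.6 × 0.37 = 3.55. A false difference toward the better-recalled side appears in 26.9% (13.8% corrected), against 2.6% (0.9%) in that direction with full capture.

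**The case against.** **The omission is not established.** A reader might infer that the trial makes no early safety record at all. The documents do not support that. The readable text is a summary table, and the section where procedures would be expected shows only a heading. The schedule sentence is also broken, so applying it to the objective reactions is the likeliest reading, not a certain one. This stands, and the point is therefore conditional.

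**The tests are not uninformative on every reading.** That description fits only a present-at-visit record. With good, equal recall since the last session, much of the information survives (46% to 55%, against 67%). This stands.

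**Bias from different durations.** It is tempting to add that, if one device's reactions last longer, a week-4 record would produce a false difference or reverse the order. Sizeable effects of that kind need something like 30% to 50% of reactions on one side still present at day 28. Such reactions do not resolve within days, and a week-4 difference in them is a real difference in persistence. For short-lived reactions both sides sit near zero. The bias that remains for them is unequal recall.

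**Pain.** A reader might conclude that the pain comparison is lost. Pain has its own paired t test, so a score taken at the session is a natural reading. No time is stated, so this needs confirming; no loss can be claimed.

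**Small sample.** Even full capture gives only 67% in the illustration, so part of the risk of a null result comes from 16 patients, not from timing. This stands, but it does not explain the fall to 1.8%.

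**Conclusion.** The point holds conditionally, with medium confidence. It is a cheap improvement to the safety comparison and does not threaten the efficacy purpose. On the readable schedule, the first record after any session is at about day 28, without a recall period. Unless the Research process section adds an earlier one, the chi-squared tests of short-lived reactions will either find almost nothing (present at visit) or depend on memory up to 4 weeks old, with some loss of power and exposure to false differences if recall differs between the sides.

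The sizes illustrate the mechanism and are not estimates for this trial. They rest on assumed rates, persistence and recall, on reactions resolving within days, and on sides treated as independent. The size of the false-difference risk also depends on whether a continuity correction is used, which the plan does not say. Long-lasting reactions remain observable at 4, 12 and 24 weeks.

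**What to change.** First check the full Research process section. If it already provides an early record, state its times and tie the tests to them. If not:

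1. At each of the three existing sessions, record for each eyelid the pain and burning during or just after the procedure, and the visible reactions before the patient leaves.
2. Name these values as the data for the pain test and for the tests of short-lived reactions.
3. State that the 4-, 12- and 24-week records cover reactions present at the visit and are taken before any treatment that day.
4. If patients are also asked about the time since the last session, define that period and analyse those reports separately.

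**Cost.** A few minutes at each existing session and slightly more data to handle, with no new visits and no change to treatment. One drawback is that same-day records may be less well blinded if the operator makes them. The readable text does not say who assesses, so the plan should state who makes the record.

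### Scarring and pigment change are not among the named adverse reactions, although the plan excludes apparently scar-prone patients, enrols only Fitzpatrick III-V skin and follows patients to 24 weeks

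*Combined protocol and SAP*

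**What the plan says.** All of the relevant text is in section 一, Research Program. The safety indicators in the Efficacy evaluation row name seven objective reactions, "Objective adverse reactions-erythema, pimples, edema, exudation, bleeding, crusting, infection", and four subjective ones, "Subjective adverse reactions-pain, burning, itching, dryness". The Treatment options row gives the objective list again, "objective adverse reactions (erythema, pimples, edema, exudation, bleeding, scabbing, infection", with one word changed and the content the same. Recording is planned before treatment, 4 weeks after each session, and 12 and 24 weeks after the third. The Statistical methods row assigns the subjective and objective reactions to a chi-square test.

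Two eligibility criteria bear on the point. Inclusion criterion 2 is "Fitzpatrick III-V". Exclusion criterion 5 begins "Scar physical, pregnancy, bilateral asymmetrical eye bags"; its first item is most naturally read as a scar-prone constitution. The only VISIA measures named are "Wrinkles, texture and pores by VISIA", and they are listed under effectiveness. The design is a "Randomized, double-blind, self-controlled study" in 16 patients.

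**The concern.** The plan treats scarring as relevant when it selects patients but does not name it as an outcome. It also restricts entry to three skin types in which, on general clinical reasoning, a reviewer would want pigment change recorded after an energy-based procedure. Follow-up to 24 weeks after the last session is long enough for a mark still visible at that point to be seen and noted.

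The trial compares two cosmetic treatments on visible facial skin, so a lasting mark from one device would matter to anyone choosing between them. If the forms follow the lists, scarring and pigment change have no named place in the safety data and no planned comparison. Two devices that differed on them could then be reported with similar safety tables.

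**Working it through.** The plan gives no rate, significance level or power for adverse reactions, so it has no figure to reproduce. The check is first a reading of the text and then an illustration of what 16 patients could show.

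**Text check.** Scarring, hyperpigmentation and hypopigmentation appear in:
- 0 of the 7 objective reactions, in either row;
- 0 of the 4 subjective reactions in the safety indicators;
- 0 of the 4 effectiveness indicators (satisfaction, VISIA, 3D data, ultrasound volume). The named VISIA measures include no pigment index.

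Because the same seven objective items appear in two rows, the omission is not a slip in one place. Neither list has an entry for other reactions.

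**Inputs for the illustration.** n = 16 eyelids per device, from the 16 patients stated in the plan and on the reading that each patient has one eyelid treated with each device. The rates p = 5%, 10% and 20% are assumed. Patients are taken as independent.

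**Would a case be seen?** P(at least one) = 1 − (1 − p)^16.
- p = 0.05: 1 − 0.95^16 = 0.56
- p = 0.10: 1 − 0.90^16 = 0.81
- p = 0.20: 1 − 0.80^16 = 0.97

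At a lower assumed rate of 2% the figure is 0.28.

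**What would no cases mean?** With 0 of 16, the one-sided 95% upper limit is 1 − 0.05^(1/16) = 0.171. The upper end of the two-sided 95% interval is 1 − 0.025^(1/16) = 0.206.

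**Could the devices be separated?** Take an exact paired test at an assumed two-sided 5% level. With all discordant pairs in one direction, five give p = 2 × 0.5^5 = 0.0625 and six give p = 2 × 0.5^6 = 0.031, so at least six are needed. Suppose that the event occurs at rate p with one device and never with the other. Every event is then a discordant pair in the same direction, and the chance of six or more in 16 is the binomial tail:
- p = 0.05: 0.008%
- p = 0.10: 0.3%
- p = 0.20: 8%

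So the trial could well observe such events, but it would rarely show a statistically significant difference between the devices.

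**The case against.** The strongest reply is that the available document is a summary. It never says the lists are exhaustive, no case report form is available, and section 二, Research process, is a bare heading. An investigator might note other events. This stands to the extent that the documents do not show that scarring and pigment change could not be recorded. They show that these events are not named and that nothing in the available text provides for them.

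A reader might infer that lasting harms in general go uncounted. The documents do not support that. The listed reactions are assessed at 12 and 24 weeks, so erythema or itching that persisted would be recorded. A surface scar might also show in the VISIA texture or 3D data, and the Statistical methods row refers to VISIA indices without listing them, so a further index cannot be ruled out.

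The pigment argument also goes beyond the text. The plan states the skin types but attaches no risk to them. The scarring argument rests on the plan's own exclusion, although the translated wording is unclear, and excluding scar-prone patients would if anything lower the rate among those enrolled. Neither criterion supports the assumed 5% to 20% rates.

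Finally, the stated purpose is to compare efficacy, and no efficacy result changes. That limits the weight of the point but does not remove it, because the plan does set out to compare adverse reactions and its list determines what is compared.

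**Conclusion.** The point holds in a limited form. Both lists omit scarring, hyperpigmentation and hypopigmentation, so the safety comparison as written does not cover them. This is more than missing detail, because a plan followed to the letter would produce no data on these events by device.

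A reader might also infer that adding the items would let the trial show which device is safer. The arithmetic says otherwise: even at an assumed 20% against 0%, the chance of a significant paired result is about 8%. The gain is descriptive. The trial could show that events occur, and with no events it could say only that a rate above about 17% is unlikely (one-sided 95% limit).

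The conclusion rests on three assumptions: that the first item of exclusion criterion 5 means scar-prone patients; that pigment change is a reasonable concern in the enrolled skin types; and that no unseen form or procedure already collects these events. It is a worthwhile, inexpensive improvement and does not threaten the main comparison.

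**What to change.** Add scarring, hyperpigmentation and hypopigmentation to the objective reactions in both the Treatment options row and the safety indicators, so that the two lists stay aligned. Record each one per eyelid, present or absent, by direct inspection at baseline and at the existing follow-up visits. The VISIA images can serve as support if they prove usable for this; the plan does not say that they yield a pigment measure.

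Report the results by device as paired descriptive data: for each item, the number of patients with the event on both eyelids, on one device's side only, on the other's only, and on neither. Give the exact upper limit where no events are seen, so that an empty row is not read as evidence of no risk.

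The cost is three more form items at visits already planned and a few more descriptive rows in the safety table. No new visit, procedure or patient is needed.

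### If device is randomized to side, the plain paired tests leave a systematic left-right difference in the error term; comparing the two side-allocation groups would recover the lost power at almost no cost

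*Combined protocol and SAP*

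**What the plan says.** All references are to the Combined protocol and SAP, section 一、 Research Program.

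- **Type of study row:** "Randomized, double-blind, self-controlled study". The row does not say what is randomized or how.
- **Treatment options row:** "16 patients with blepharoplasty bags", whose "two bilateral blepharoplasty bags were treated with laser respectively". Which device goes to which side is not stated, and neither is any balance between sides.
- **Statistical methods row, pain:** "The pain of the left and right lower eyelids was tested by paired t" test.
- **Statistical methods row, imaging outcomes:** "changes of various indexes of visia, 3D, and ultrasound were compared with the Wilcoxon symbol rank test of paired samples".
- **Inclusion and Exclusion Criteria row:** patients with "bilateral asymmetrical eye bags" are excluded.

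No side term, stratification by side or comparison of allocation groups appears. No alpha, power, effect size or standard deviation accompanies the 16 cases.

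**The concern.** In a split-face trial each observation carries two factors, device and side. Suppose microneedles go on the left in some patients and on the right in the others. The microneedle-minus-laser difference is then the device effect plus the general left-right difference in the first group, and the device effect minus it in the second. A plain paired test treats that plus-or-minus term as random noise. Balanced allocation removes it from the estimate but not from the estimated variance. The situation matches a crossover trial analysed without its period effect.

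What is at stake is power. With 16 pairs and no power calculation in the documents, there is little to spare.

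**Working it through.** **Inputs.** From the documents: 16 patients, within-patient comparison, paired t test for pain, signed-rank test for changes in VISIA, 3D and ultrasound. Assumed because the documents are silent: two-sided alpha 0.05, device randomized to side, an 8:8 split (simple randomization is also checked), normal errors, and a device effect of 0.749 SD of the paired difference. That effect gives the paired t test 80% power at 16 pairs. The left-right difference is varied from 0 to 1.0 SD. The 16 cases cannot be reproduced, because no inputs are given for that number.

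**Model.** d = τ + sλ + e, where d is microneedle minus laser, τ the device effect, λ the left-minus-right difference, s = +1 with microneedles on the left and −1 with them on the right, and e has variance σ².

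**Variance.** At 8:8 the mean of d estimates τ without bias, and its true variance is σ²/16. The paired t test, however, estimates the variance of d as, on average, σ² + λ²·16/15. With σ = 1:

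- λ = 0.25: 1 + 0.0625 × 16/15 = 1.07
- λ = 0.50: 1 + 0.25 × 16/15 = 1.27
- λ = 0.75: 1 + 0.5625 × 16/15 = 1.60
- λ = 1.00: 1 + 1 × 16/15 = 2.07

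**Accounting for side.** Left minus right averages λ + τ with microneedles on the left and λ − τ with them on the right. The group difference is 2τ, so half of it estimates τ and λ cancels. The residual variance returns to σ², with 14 degrees of freedom instead of 15.

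**Power by simulation** (100,000 trials per setting for the t tests, 20,000 for signed-rank):

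| λ (SD) | Paired t | t, side accounted for | Signed-rank |
|---|---|---|---|
| 0 | 79.9% | 79.5% | 76.8% |
| 0.25 | 78.0% | 79.5% | 74.1% |
| 0.50 | 72.0% | 79.3% | 67.6% |
| 0.75 | 62.0% | 79.6% | 56.2% |
| 1.00 | 49.1% | 79.8% | 41.0% |

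The rank-sum test on left-minus-right differences has power of 77 to 78% for λ from 0 to 0.75.

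**Other device effects.** At 0.5 SD, paired t power falls from 46.6% (λ = 0) to 37.0% (λ = 0.5), against about 46% with side accounted for. At 1.0 SD it falls from 96.2% to 93.3%, against 96%.

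**Break-even for the t test.** The two-sided critical values are 2.131 (15 df) and 2.145 (14 df). The squared ratio is about 1.013, so the variance inflation exceeds the price of the lost degree of freedom once λ²·16/15 is above about 0.013, or λ above about 0.11. The simulation agrees: at λ = 0.10 the two analyses have 79.6% and 79.5% power, and at 0.15 they have 79.3% and 79.6%.

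**Type I error of the paired t test.** With a forced 8:8 split it is 4.9%, 4.3%, 3.0% and 1.5% at λ = 0, 0.25, 0.5 and 0.75. With simple randomization of side it stays between 4.9% and 5.1%, but power is still lost (70.6% at λ = 0.5).

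**Unequal split.** At 10:6 the plain estimate moves by (10 − 6)/16 × λ = 0.25λ. This is chance imbalance given the allocation obtained. Averaged over random allocation it is zero.

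**The case against.** The case against raising this is substantial.

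- **The premise is only implied.** No row says that device is randomized to side. If device is fixed to side, the two are confounded and no side term can be estimated. This stands, and the point is conditional on it.
- **The pain sentence contrasts left with right, not device with device.** The contrast and the allocation have to be defined first. This also stands. The point is a refinement that applies once the contrast is written by device.
- **The size is assumed.** A reader might infer that losses of 8 to 18 points are to be expected here. The documents do not support that: they report no left-right difference, and such losses need one of 0.5 to 0.75 SD. At 0.25 SD the t test loses about 2 points.
- **The plan has some protection.** Excluding asymmetric eye bags, and analysing changes for VISIA, 3D and ultrasound, should shrink static side differences. A side difference in response can remain. Pain is not described as a change, so it lacks the second protection, although the plan lists it as a safety measure.
- **The plain test is valid.** A reader might infer a biased estimate or an inflated false-positive rate. Neither follows under randomized allocation: type I error is at or below about 5%. Nor is the test always conservative, because that needs a forced 8:8 split, which the plan does not state.
- **Not every left-right difference costs net power.** Any such difference enters the error term, but below about 0.1 to 0.15 SD the lost degree of freedom cancels the gain for the t test.

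**Conclusion.** The point holds as one of efficiency, conditional on device being randomized to side, and it is minor. Under the stated assumptions (16 pairs, 8:8, device effect about 0.75 SD, two-sided 0.05), ignoring side costs the t test about 2, 8 and 18 points of power at left-right differences of 0.25, 0.5 and 0.75 SD (80 − 78, 80 − 72, 80 − 62). The signed-rank test loses about 3, 9 and 21 points relative to no side difference (76.8 − 74.1, 76.8 − 67.6, 76.8 − 56.2), while the rank-sum alternative stays at 77 to 78%. Whether the trial would see a loss of that order cannot be told from the documents. The change is worth making because it costs almost nothing and turns the plan's left-right contrast into a test of device.

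**What to change.** State that device is randomized to side and how, and record which side received each device. Then analyse by allocation group:

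- Form left minus right within each patient and compare patients with microneedles on the left with those with microneedles on the right. Use a two-sample t test for pain and a Wilcoxon rank-sum test for the VISIA, 3D and ultrasound changes.
- Report half the group difference as the device effect. For the t test, an equivalent form is to regress the microneedle-minus-laser difference on side coded +1/−1 and test the intercept; at an 8:8 split the two give the same result.

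The cost is a sentence or two of analysis wording and one degree of freedom. If there is no side difference, that is about half a point of t-test power; the rank-sum test loses none against the signed-rank test in these settings. No extra measurements are needed. If device is fixed to side, this analysis is not available, and the confounding of device with side would have to be dealt with in the design.
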